**CINCINNATI CHILDREN’S HOSPITAL MEDICAL CENTER
INSTITUTIONAL REVIEW BOARD – Protocol**
and
Community Health Center, Inc IRB
Protocol Template (HRP-212)

1) Protocol Title

Rx for Success: A Randomized Controlled Trial of Technology-Based Dialogic Reading Training Incorporated Into Reach Out and Read

2) Principal Investigators

Overall: [name], MS MD FAAP
Cincinnati Children’s Hospital Medical Center
Division of General and Community Pediatrics
Reading and Literacy Discovery Center

On-site at CHC: [name], MD
Community Health Center at Connecticut Children’s Hospital

Other staff: [name] (coordinator, CCHMC), [name] MD (co-I, CCHMC), [name], PhD (consultant, Reach Out and Read National Office (MA)), [name] (consultant, Children, Inc.). A primary research coordinator will be hired to conduct this study at the primary care clinical site in CT.

3) Funding Source

The Carol Ann and Ralph V. Haile, Jr./U.S. Bank Foundation
The Grossman Family Foundation

4) Objectives*

Specific Aim 1 (Rx for Success; RS): To explore the efficacy of incorporating dialogic reading training via the RS application into ROR during well-child visits for infants (6-12 months old) and toddlers (18-24 months old), compared to standard ROR practice.

Hypothesis 1a (language): Language scores (LENA Snapshot) will be higher in children whose caregivers are provided with the RS app.

Hypothesis 1b (social-emotional): Social-emotional development scores (DECA-I/T items) will be higher in children whose caregivers are provided with the RS app.

Hypothesis 1c (dialogic quality): Dialogic reading quality scores (DialogPR-I/T) will be higher in caregivers presented with the RS app.

Hypothesis 1d (attitudes): Attitudes towards shared reading at home (items from StimQ-P READ and PVR) will be higher in families provided with the RS app.

Specific Aim 2 (exploratory):

Hypothesis 2a: Reported screen-based media use (ScreenQ) will be lower in families provided with the RS app, reflecting greater emphasis on interactive shared reading.

Hypothesis 2b: Language (LENA Snapshot) and social-emotional (DECA-I/T items) scores will be higher for children with less reported screen-based media use (ScreenQ).

5) Background*

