during regularly scheduled well-child visits. This study will be powered based on the primary language outcome measure (LENA Snapshot). For a two-group (intervention/control), pre-post repeated-measure analysis with two age categories (6-12 months, 18-24 months), an ANCOVA model will be applied for both age categories and their interaction, to assess the difference in language scores between intervention and control groups. For this study, at least 180 subjects will be needed to have 80% statistical power to detect slightly greater than medium effect size (Cohen $f=0.30$), controlling for the baseline pre-measurement with a two-sided significance level of 0.05. This effect size was determined considering the 2008 National Early Literacy Panel Report, which examined 16 studies and reported an effect size of 0.6 for dialogic reading on language outcomes ($d=0.6$; Shanahan, et al).⁴⁹ A separate meta-analysis of 18 studies that tested dialogic reading intervention found average effect size for language outcomes and vocabulary of 0.29 and 1.02, respectively.⁸ However, these reports largely involved preschool- and school-age children, and no studies to our knowledge have reported effect sizes of dialogic reading for language in infants and toddlers.

We anticipate that full enrollment for this study within 6 months is feasible given historical well-visit volumes for these ages (40/month meeting enrollment criteria) at the participating clinic at CHC@CCMC. The CRC will optimize enrollment efficiency factoring scheduled well-visit volumes and demographic needs (age), via weekly communication regarding clinic schedules with clinic managers. The CRC will identify the arrival and registration of potential participants by monitoring the daily schedule (in Centricity) to identify well child visits for children of the appropriate age groups, and will greet them in the waiting room. For enrolled patients only, the CRC will also monitor scheduled encounters (in e-Clinical Works) to identify upcoming appointments for the follow-up (post-intervention) visit, and will monitor arrival in Centricity. The CRC will approach families in the waiting area, confirm that the child meets inclusion criteria by age, and present the major aims of the study in plain language:

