- Comfortable speaking English during their WCC and reviewing/comprehending study materials without a translator, including informed consent.
- Functional literacy in at least one primary caregiver, defined as the ability to navigate the RS application, read prompts provided by the RS application (targeted 6th grade reading level as estimated via the Readable.io website), and understand/provide informed consent, administered in English.
- Possession of a smartphone or tablet device capable of downloading, installing and utilizing the RS application.

Twins will be excluded from the study, to minimize confounding.

In the case of 2 eligible siblings presenting at the same visit (i.e. 6 month old and 18 month old), both may be enrolled, though will be randomized to the same group to minimize confusion and confounding.

In the case of an eligible sibling presenting after another sibling has been enrolled, this second child (and any other siblings) will be ineligible, to minimize confounding via a training effect.

b) Study Endpoints*

Outcomes of interest for this study (6 months post-intervention) are as follows:

a) **Descriptive Statistics:** Descriptive statistics will be used to summarize parent-child demographics, language and social-emotional testing scores (LENA Snapshot, DECA-I/T excerpted items), home reading environment/dialogic reading/cognitive-language attitudes (StimQ-P READ and PVR excerpted items, DialogPR-I/T), and screen time (ScreenQ). Group-wise comparisons will be performed to determine any differences

between randomization groups. Spearman's rank correlation will then be used to assess correlation between variables of interest at baseline and 6-month follow-up visits, applying age and gender as covariates.

b) **Pre-post intervention cognitive-behavioral outcomes:** Outcomes of interest will involve group-wise statistical comparisons pre-post intervention of language, social-emotional development, and home reading practices/attitudes measures. All repeated measures (LENA, DECA-I/T excerpted items, StimQ READ and PVR excerpted items, DialogPR, ScreenQ, reading attitudes) will be examined via paired t-test, Wilcoxon signed-rank test, and McNemar's tests. Association between home reading environment and screen time and language and social-emotional testing scores will be assessed by correlation coefficient and applied in general linear regression models, applying age and gender as covariates.

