Power Analysis: We will recruit 248 children in 2 age categories: approximately 6 months old (infants, n=124), and approximately 18 months old (toddlers, n=124) via convenience sampling in the CCMC clinic waiting room during regularly scheduled well-child visits. This study will be powered based on the primary language outcome measure (LENA Snapshot). For a two-group (intervention/control), pre-post repeated-measure analysis with two age categories (6-12 months, 18-24 months), an ANCOVA model will be applied for both age categories and their interaction, to assess the difference in language scores between intervention and control groups. For this study, at least 180 subjects will be needed to have 80% statistical power to detect slightly greater than medium effect size (Cohen $f=0.30$), controlling for the baseline pre-measurement with a two-sided significance level of 0.05. This effect size was determined considering the 2008 National Early Literacy Panel Report, which examined 16 studies and reported an effect size of 0.6 for dialogic reading on language outcomes ($d=0.6$; Shanahan, et al).⁴⁹ A separate meta-analysis of 18 studies that tested dialogic reading intervention found average effect size for language outcomes and vocabulary of 0.29 and 1.02, respectively.⁸ However, these reports largely involved preschool- and school-age children, and no studies to our knowledge have reported effect sizes of dialogic reading for language in infants and toddlers.

Confidentiality will be maintained by storing all data on secure, password-protected servers hosted by the Cincinnati Children's Division of Biomedical Informatics. The CRC at CHC@CCMC will log in to this database via a password to enter study data, as is

customary for off-site studies. REDCap software will be used for data capture and is a secure, HIPAA-capable web-based data management tool, and is provided at no cost by Cincinnati Children's via a grant to its Center for Clinical and Translational Science (CCTST). Access to REDCap data and the servers is limited to personnel directly involved in the study. All hard copy records including consent forms will be securely stored by the CRC at CHC@CCMC, access restricted to study related personnel. All potentially identifying data will be destroyed within 3 years of study completion.

e) Provisions to monitor the data for the safety of subjects*

This study involves minimal risk, and such provisions are not required.

f) Withdrawal of subjects*

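### For the non-language outcomes (Hypotheses 1b–1d and exploratory 2a), the tests named in Protocol section 8b, item b are within-family tests and cannot compare the RS arm with control

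*Protocol*

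**What the plan says.** **Hypotheses (section 4).** Each of 1b, 1c, 1d and 2a is a contrast between randomized arms. For example, 1b reads: "Social-emotional development scores (DECA-I/T items) will be higher in children whose caregivers are provided with the RS app". Hypotheses 1c and 1d make the same kind of claim for DialogPR and for StimQ items/attitudes. Exploratory 2a predicts lower ScreenQ with the app.

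**Section 8b, item a (Descriptive Statistics).** After listing these measures, it states: "Group-wise comparisons will be performed to determine any differences" "between randomization groups" (one sentence, split by a page break). No test is named.

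**Section 8b, item b.** It opens: "Outcomes of interest will involve group-wise statistical comparisons pre-post intervention", for language, social-emotional development and home reading practices/attitudes. All repeated measures, including LENA and ScreenQ, then "will be examined via paired t-test, Wilcoxon signed-rank test" and McNemar's tests. A last sentence relates home reading and screen time to the child scores, "applied in general linear regression models, applying age and gender as covariates". Randomized arm is not named there.

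**Power sections (8a and 8d).** Both say "an ANCOVA model will be applied for both age categories and their interaction", and both give its purpose as "to assess the difference in language scores between intervention and control groups". This is the only between-arm model in the protocol, and it is tied to language.

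**The concern.** The paired t, Wilcoxon signed-rank and McNemar tests ask whether families changed over six months. The hypotheses ask whether families given the app ended up different from those not given it. Children are six months older at follow-up, the same questionnaires are repeated, and both arms receive customary ROR, so change shared by the arms is plausible. For ScreenQ, the control arm also receives a book on limiting screen media, so a within-arm change there is especially hard to read.

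Pooled over arms, a paired test measures shared change. Run separately by arm, it yields two p-values whose comparison is not a test of the arm difference. With modest shared change, one arm can cross 0.05 and the other miss it by chance. With large shared change, both arms are significant and a real RS effect is hidden.

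**Working it through.** **1. What each named analysis can test**

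| Analysis in the protocol | Outcomes covered | Contains randomized arm? |
|---|---|---|
| ANCOVA (8a, 8d) | Language scores only | Yes |
| Group-wise comparisons (8b, item a) | All measures | Yes, but no test named |
| Paired t, signed-rank, McNemar (8b, item b) | All repeated measures | No |
| Linear regression (8b, item b) | Home reading and screen time against child scores | Not named |

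No named test performs the comparison in 1b–1d or 2a.

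**2. The protocol's own figure.** The stated minimum of 180 belongs to the language ANCOVA. For a one-degree-of-freedom arm contrast with one covariate, f = 0.30 and two-sided 0.05, noncentral F with λ = f²N gives 80.4% power at N = 90. Taken once per age category, 2 × 90 = 180; with 10% attrition, 180/0.9 = 200. Both stated figures reproduce, and this point disputes neither.

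**3. Size of the problem if within-arm p-values were compared**

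Inputs from the protocol: 62 per arm in each age category; 10% attrition, so 62 × 0.9 ≈ 56 per arm (124 × 0.9 ≈ 112 with the age categories combined); two-sided 0.05.

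Assumptions, because the protocol gives none of these: the decision rule (significant in RS, not in control), pre-post correlation r, and a shared change δ in baseline SD units in the favourable direction. There is no RS effect.

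- SD of change = √(2(1 − r)). At r = 0.6 this is 0.894.
- Noncentrality of the paired t = δ√n / SD of change. At δ = 0.2 and n = 56: 0.2 × 7.483 / 0.894 = 1.673, with critical value 2.004.
- P(RS significant in the favourable direction) = 37.6%; P(control not significant) = 62.4%.
- P(RS only) = 0.376 × 0.624 = 23.5%.

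The product is essentially p(1 − p), so its ceiling is 25%, at p = 0.5.

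| Shared change (SD) | 0 | 0.1 | 0.2 | 0.25 | 0.3 | 0.5 |
|---|---|---|---|---|---|---|
| RS only, n = 56, r = 0.4 | 2.4% | 8.9% | 19.6% | 23.8% | 25.0% | 7.5% |
| RS only, n = 56, r = 0.6 | 2.4% | 11.1% | 23.5% | 24.9% | 21.3% | 1.6% |
| RS only, n = 56, r = 0.8 | 2.4% | 16.7% | 23.0% | 14.2% | 5.9% | 0.0% |
| RS only, n = 112, r = 0.6 | 2.4% | 16.9% | 22.7% | 13.8% | 5.6% | 0.0% |
| Control not significant, n = 56, r = 0.6 | 95.0% | 87.0% | 62.4% | 46.2% | 30.6% | 1.6% |

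Over r = 0.4 to 0.8 and n = 56 or 112, the peak stays at 25% and falls at a shared change between 0.12 and 0.29 SD.

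**4. Hidden effect.** The last row needs no assumed RS effect size. Whatever the true effect, an RS-only result cannot occur more often than control is non-significant. At a shared change of 0.5 SD that limits detection to 1.6% (8.1% to 0.0% for r = 0.4 to 0.8); at 0.3 SD, to 30.6% (47.9% to 6.3%).

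**5. Comparison with ANCOVA.** Regressing follow-up on arm and baseline, with no arm effect, gave simulated rejection rates of 4.5–5.2% two-sided and 2.1–2.7% in favour of RS. The settings were r = 0.4/0.6/0.8, shared change 0/0.2/0.5 SD and n = 56 and 112, with 20,000 trials each.

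**The case against.** The strongest reply is that the paired-test list is not the efficacy analysis. LENA is on the same list and also has an ANCOVA, so the list can coexist with a separate arm comparison. Item a promises that comparison for every measure concerned, and naming a test for secondary outcomes is commonly left to the SAP, which is not shown. The opening phrase of item b could also mean a pre-post comparison within each group, which paired tests do perform.

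Part of this stands. The intent to compare arms is on record, and the primary analysis is sound. But the point is not that a test is missing: the protocol does name tests for these outcomes, and they do not answer its hypotheses. A SAP that follows item b inherits the mismatch; one that departs from it contradicts the protocol. On the within-group reading, item b has no arm comparison at all.

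Three smaller objections are fair. Screen time is absent from the opening sentence of item b, so for 2a the promised comparison comes from the hypothesis and item a. The error rates depend on a rule the protocol does not state. They also count only favourable shared change: an unfavourable shift of 0.1 SD would give an RS-only rate of about 0.2% at n = 56 and r = 0.6. None of these supplies the missing arm contrast.

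**Conclusion.** The concern holds, with high confidence, and should be fixed. That the named tests cannot compare the arms follows from their form and needs no assumption. The 25% ceiling and the bounds on detection do rest on the assumed decision rule, correlation and shared change; they show what could go wrong, not what this trial plans or will see. The consequence is confined to Hypotheses 1b–1d and exploratory 2a. The LENA ANCOVA and the sample size are not in question.

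**What to change.** In section 8b, item b, state that the efficacy analysis of each non-language outcome is a between-arm comparison adjusted for the baseline value of the same measure and for age category.

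- **Total scores** (DECA five-item sum, DialogPR, ScreenQ): use the ANCOVA form already named for LENA, fitted within age category where the infant and toddler versions differ.
- **Items analysed singly** (StimQ items, whether reading is among the favourite activities): use a logistic or ordinal model with an arm term.
- **Paired t, signed-rank and McNemar tests**: label them as within-arm description only. Apply the same label to LENA so that its ANCOVA is clearly the efficacy analysis.

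The cost is protocol wording and minor analysis work. Baseline and follow-up values are already collected on every measure, so no new data and no change in sample size are needed.

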Literacy is a major public health issue, the cost of low attainment estimated at over \$300 billion in the United States and over \$1.2 trillion worldwide, disproportionately affecting low-socioeconomic status (SES) populations.²⁹ While an estimated 5-12% of reading difficulty has an organic cause (e.g. dyslexia),³⁰ the majority is attributable to inadequate resources, motivation and/or stimulation required to learn to read.²⁹ As of 2015, 64% of US 4th graders scored below proficient in reading, largely unchanged from prior reports,²⁸ and scores skewed lower for low-SES and minority children.^{28,31} The seeds of environmental reading difficulty are planted early; many children arriving at school at a substantial disadvantage in readiness and increasingly unlikely to catch up with peers as academic demands accelerate.^{31,32} Environmental illiteracy is considered “heritable,” fueling cycles of poverty and poor academic, vocational and health outcomes.³³ Prevention and early intervention offer tremendous cost savings in terms of health and productivity.³⁴⁻³⁶

The American Academy of Pediatrics (AAP) recommends literacy promotion in primary care settings beginning at birth, and increased funding for reading promotion programs such as ROR, provider training, and research.⁴ The bases for these recommendations are enduring cognitive, social-emotional and neurobiological^{20,37} benefits of nurturing shared reading environments during the critical developmental span of early childhood.⁴ Children’s books serve as catalysts for verbal and social-emotional engagement^{26, 38, 39} and foster positive attitudes towards reading.^{4,40} However, the *quality* of shared reading tends to moderate - or negate, if deficient - these important benefits.^{13,21} Dialogic reading is a method of shared reading developed to promote reciprocal dialogue between a caregiver and child,⁸ particularly in low-SES households where such dialogue is often lacking.⁶ Behavioral evidence suggests that dialogic reading may confer substantial cognitive benefits beginning in infancy,^{10,11} including oral language,^{12,13} narrative comprehension,¹⁴ print concepts,¹² and attention¹⁵ - foundational emergent literacy skills.¹⁶ Social-emotional benefits have also been shown, including increased parent-child bonding, pro-social behavior¹¹ and enjoyment of reading.^{17,18}

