particularly demographics, home reading/language environment (StimQ READ/PVR items), language (LENA), and social-emotional development (DECA excerpted items).

Estimated testing/survey administration time is approximately 17 minutes.

Administered at baseline (pre-intervention; approximately 6 and 18 months old):

1) **Demographic Surveys (3 minutes):** During the first visit only, demographic information will be obtained from custodial parents including contact information, type of smartphone or tablet to be utilized including data plan (e.g. unlimited vs limited data), household income, parental education, history of reading difficulty including dyslexia or functional illiteracy, who usually reads to the child at home, primary language spoken at home, daycare attendance, and number of occupants in the home. Estimated administration time for this survey is 3 minutes.

2) **LENA Snapshot (6 minutes)** is a validated, 52-item, evaluation of language skills for infants and toddlers by parental report focusing on well-established milestones associated with expressive and receptive language skills, with a standardized score under 77 suggesting risk for delay. It provides developmental age and percentile ranking information compared to age-matched peers. Correlations with standard measures such as PLS-4 and test-retest correlations average 0.93. Estimated administration time is 3 minutes. Of note, this measure is not directly administered to the child.

[figure not shown]
3) **Devereux Infant/Toddler Early Childhood Assessment (DECA-I/T items; 2 minutes)** is a measure of social and emotional health validated for use in children between 1 month through 36 months, which are strength-based, nationally standardized, and easy to use. The DECA has 4 scales: Attachment/Relationships (18 items), Initiative (11 items), Self-Regulation (7 items), and Total Protective Factors composite. The infant form (1-18 months old) has 33 items, and the toddler form (18-36 months old) has 36 items. *To keep our administration time as brief as possible, we will excerpt 5 items from the attachment subscale* (those most likely to be influenced by shared reading) for this study, and add these item scores to determine a total score. Estimated administration time for these items is 2 minutes.

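### The models for exploratory Hypothesis 2b name only age and gender as covariates, so the screen-use association cannot be read as independent of family background or, at follow-up, of trial arm

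*Protocol*

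**What the plan says.** Section 4 of the Protocol (Objectives) places Hypothesis 2b under Specific Aim 2, which it labels exploratory. The hypothesis reads: "Language (LENA Snapshot) and social-emotional (DECA-I/T items) scores will be higher for children with less reported screen-based media use (ScreenQ".

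Section 8b (Study Endpoints) gives the analysis. Item b says the association of home reading environment and screen time with the language and social-emotional scores will be "assessed by correlation coefficient and applied in general linear regression models, applying age and gender as covariates". Item a sets Spearman correlations to "assess correlation between variables of interest at baseline and 6-month follow-up visits, applying age and gender as covariates". Neither item names a further covariate, and no other section adds one for these models. The ANCOVA in sections 8a and 8d concerns the arm comparison on language, not 2b.

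Three other places bear on the choice of covariates:

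- Section 8c, Demographic Surveys, collects "household income, parental education, history of reading difficulty including dyslexia or functional illiteracy" at the first visit.
- Section 5 (Background) says of US fourth-grade reading that "scores skewed lower for low-SES and minority children".
- Hypotheses 1a, 1b and 2a in section 4 predict that the app raises language scores, raises social-emotional scores and lowers ScreenQ.

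**The concern.** Families are randomised to the app, not to an amount of screen time, so 2b is an observational comparison inside a trial. A variable that moves both ScreenQ and the child's score will create or distort an association between them unless the model accounts for it.

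The Protocol supplies two candidates. One is socioeconomic status (SES), which the Background treats as a driver of literacy outcomes and which the study measures through income and education. The other is arm: if Hypotheses 1a, 1b and 2a are all true, arm is a common cause of both sides of the 2b association in follow-up data pooled over arms.

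At stake is what a result on 2b can be taken to mean. Sections 5 and 7 say the study is to provide data for a larger longitudinal study. A screen-use association adjusted only for age and gender could be carried into that design as if it were independent of family circumstances.

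**Working it through.** **The plan's own figures.** The Protocol gives no sample size, power or expected correlation for 2b, so there is no figure for it to reproduce. The sample sizes below come from sections 8a and 8c. At least 180 subjects are needed; with 10% attrition this becomes 180 / 0.90 = 200; planned enrolment is 248.

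**Assumptions not in the documents.** SES correlates with ScreenQ and with the score by the same size a (opposite signs), with a = 0.2, 0.3 or 0.4. Screen use has no direct association with the score. The test is two-sided at 5%.

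**Step 1, induced correlation.** A common cause induces a correlation equal to the product of its two correlations, so its size is a × a:

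- 0.2 × 0.2 = 0.04
- 0.3 × 0.3 = 0.09
- 0.4 × 0.4 = 0.16

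**Step 2, chance of a significant result at n=200.** By Fisher's z, SE = 1/√(200 − 3) = 0.0713. The critical z is 1.96 × 0.0713 = 0.1396, which is |r| = 0.139. The rejection probability is Φ((z − 0.1396)/0.0713) + Φ((−z − 0.1396)/0.0713), where z = arctanh(induced r).

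- r = 0.04: z = 0.0400; Φ(−1.398) + Φ(−2.522) = 0.087
- r = 0.09: z = 0.0902; Φ(−0.693) + Φ(−3.227) = 0.245
- r = 0.16: z = 0.1614; Φ(0.305) + Φ(−4.225) = 0.620

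These are about 9%, 24% and 62%. Allowing two degrees of freedom for age and gender gives 0.087, 0.243 and 0.616, which makes no material difference.

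**Step 3, simulation at the other sample sizes.** The score was regressed on ScreenQ with age and sex, with no direct effect of screen use (4,000 runs per scenario).

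| Common cause (assumed) | N=180 | N=248 |
|---|---|---|
| SES, a = 0.2 | 8% | 9% |
| SES, a = 0.3 | 22% | 30% |
| SES, a = 0.4 | 58% | 72% |
| Arm only: d = 0.6 on language, 0.3 on screen use | 9% | 11% |
| Arm only: d = 0.6 on both | 19% | 26% |
| SES 0.3 plus arm (0.6 and 0.3) | 39% | 52% |
| SES 0.3 plus arm, opposite sign on screen use | 8% | 10% |

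The d = 0.6 for language is the literature value cited in section 8a. The arm effects on ScreenQ are assumed. Converting by r = d/√(d² + 4) gives 0.287 for d = 0.6 and 0.148 for d = 0.3, so arm alone induces 0.287 × 0.148 = 0.043 or 0.287 × 0.287 = 0.083.

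**Step 4, with the covariates added.** With SES and arm in the same regression, the rejection rate returns to 4.4% to 5.7% in every scenario. This takes SES as measured without error.

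**The case against.** The strongest reply is that 2b is exploratory and worded as an association. If family background induces a correlation of 0.16, that correlation is real and 2b as written is true. A reader might infer from the percentages above that the plan has a false-positive rate of up to 62%. The documents do not support that: the percentages are the chance of detecting an association that comes wholly through SES, and they count as errors only if 2b is read as an association independent of family background. This part of the reply stands and limits the point to interpretation.

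The sizes also rest on assumption. No section gives a correlation of SES with ScreenQ or with LENA. The Background statement concerns fourth-grade reading, not parent-reported language in infants and toddlers. Recruiting a low-SES population at one clinic probably narrows the range of income and education. This stands too.

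A reader might also infer that arm alone could produce the association 2b predicts. The documents do not settle even its direction on ScreenQ. Controls receive a book on limiting screen use (sections 8 and 8c), and section 9 says the app may increase screen use. If arm acts the opposite way on ScreenQ, it partly cancels the SES effect. Arm cannot confound baseline data at all.

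Finally, a reader might infer that the plan ignores its own time order by correlating screen use and score only within a visit. The Spearman sentence refers to the two visits, but the regression sentence names neither a time point nor pooling over arms, so this cannot be shown.

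What the reply does not remove is that the covariate set is written into the Protocol, and the measured family-background variables are not in it.

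**Conclusion.** The concern holds as a minor point about model specification. The association planned for 2b, adjusted for age and gender only, may partly reflect family background or, at follow-up, arm, and so cannot be read as independent of them.

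Its size is unknown from the documents. With assumed SES correlations of 0.2 to 0.4 with both variables and no direct association, the chance of a significant result at n=200 runs from about 9% to 62%, and the low end may be the more realistic for this sample. Arm is a weak source unless its effects on both variables are large, and it may act in either direction.

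No stated figure is wrong and no passages conflict. The primary language comparison rests on randomisation and its own ANCOVA and is not touched.

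**What to change.** In section 8b, item b, add household income and parental education to the regression of language and social-emotional scores on ScreenQ, and add arm whenever follow-up data are used. Report 2b as an adjusted association, and give the correlation and the age- and gender-adjusted result as descriptive.

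A model of the follow-up score on baseline ScreenQ, adjusted for the baseline score, may be added as a supplementary analysis. It asks a different question from 2b and should not replace the planned analysis.

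The cost is wording only, since every variable is already collected. The analysis loses several degrees of freedom, more if income or education is categorical, and needs a stated way of handling missing income. Some residual confounding will remain, because income and education measure family background imperfectly and some families may not report income.
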